11.3. Study reporting and publications

Interim and final study results will be included in safety and regulatory reports as appropriate. Study results will be made available externally through peer reviewed manuscript and conference presentation.

ANNEX 1. CASE REPORT FORM

CRF completed by: text field

CRF completed date: Year/month/day

(These two items should be included for each follow up injection and hepatotoxicity form)

Data entry instructions

Standard text reg. comma vs. full stop, test not performed, unknown dates

Link to document about data entry, contact for questions etc.

Patient ID: xxx-xxxx

Date of birth: Year/month/day

HIV subtype

Has an HIV subtype test been performed prior to initiation of long-acting antiretroviral therapy yes/no

(If yes)

Date of latest HIV subtype test prior to initiation of long-acting antiretroviral therapy Year/month/day

Subtype drop down menu with subtypes

Oral lead-in antiretroviral therapy

Drug 1 (drop down menu)

1) Cabotegravir

2) Rilpivirine

Start date Year/month/day

Vii V Healthcare Com

CONFIDENTIAL

eTrack Project Number: 215161

Stop date

Year/month/day

Was oral lead-in antiretroviral therapy stopped because the patient has initiated long-acting antiretroviral therapy

Yes/no

If yes, Treatment section below will open

If no, following will open

Reason for discontinuation protocol

Drop down menu with all reasons listed in table 2 in the

Drug 2 etc

(This section of the form refers to the first LAI)

After the first injection with long-acting antiretroviral therapy (LAI), the CRF will capture information about the following scenario's as set out below;

- 1) The patient receives LAI as planned
- 2) The planned LAI is not given, and the patient **starts bridging therapy**. After end of bridging therapy there are three possibilities:
 - a. LAI is resumed in which case we want to know date of injection, dosage etc
 - A decision to stop LAI has been made in which case we want to know why LAI was stopped
 - c. Switched to a different ART regimen
- 3) The planned LAI is not given, and the patient **does not start bridging therapy**. We want to know if the patient later restarts LAI.
 - a. LAI is resumed in which case we want to know date of injection, dosage etc
 - b. A decision to stop LAI has been made in which case we want to know why LAI was stopped
 - c. Switched to a different ART regimen

The CRF will only capture the first exposure to LAI. The second injection for the two-month schedule is given one month after the first injection and hence we will allow three months after the first injection to see if the regimen was resumed (≤2 months) or re-initiated (>2 months). In

case of resumption of LAI after missed second injection in two months or less, we will still consider it first exposure.

Similarly, the third injection (and injections thereafter) for the two-month schedule is given two months after the second injection and hence we will allow four months after the second injection to see if the regimen was resumed (≤3 months) or re-initiated (>3 months). In case of resumption of LAI after missed third injection in three months or less, we still consider it first exposure.

Treatment with long-acting antiretroviral therapy

Which long-acting antiretroviral drugs have been initiated? (drop down menu)

1) long acting cabotegravir + long acting rilpivirine

2) long acting cabotegravir without rilpivirine

3) long acting rilpivirine without cabotegravir

Dosage: 400/600 mg (CAB) / 600/900 mg (RPV) (drop down

menu)

Date of first injection: Year/month/day

Intended dosing schedule of long-acting antiretroviral therapy Monthly/Every 2 Month

HIV resistance testing (only pops up for the first injection and if CAB + RPV has been selected)

Has a HIV resistance test been performed prior to initiation of long-acting cabotegravir + rilpivirine yes/no

If yes

Date of latest most recent resistance test prior to initiation of long-acting antiretroviral therapy Year/month/day

Method used drop down menu

Please upload a copy of the resistance test report (result will be based on central review)

(After completion of date of first injection, a new section will open for second injection with target date one month after the first injection. All the questions below refer to subsequent injections after the first)

Has the patient received the next planned injection with long-acting antiretroviral drugs yes/no

If yes, Which long-acting antiretroviral drugs were given? (drop down menu)

1) long acting cabotegravir + long acting rilpivirine

2) long acting cabotegravir without rilpivirine

3) long acting rilpivirine without cabotegravir

Dosage: 400/600 mg (CAB) / 600/900 mg (RPV) (drop down

menu)

Date of injection: Year/month/day

Intended dosing schedule of long-acting antiretroviral therapy Monthly/Every 2 Month

(if the patient switches from monthly to two-monthly injections or vice versa, a new question pops up)

Reason for switching to monthly (or 2 monthly) injection schedule (drop down menu)

- 1. Convenience
- 2. To reduce cost
- 3. To reduce side effects
- 4. Personal reasons
- 5. Other (+ text field)

(After completion of date of second injection, a new section will open for third injection with target date two month/3 months [for monthly and 2 monthly schedules, respectively] after the first injection. As long as the patient receives injections as scheduled, the target date for the next injection is determined by the start date ± 1 month/2 months ± 7 days for each injection depending on schedule)

(All injections until 24 months+ six weeks after initiation of LAI will be collected)

If no to question whether planned injection has been given, following question will appear:

	Has the patient started bridging therapy?								
		YES			NO				
If yes, new question will show:									
Reason for starting bridging therapy (LAI drugs out of stock,									
1 '	•	to come for the	•						
injection site	adverse effe	t, other + text fie	ld)						
Start date:				Has th	e patient	later res	started long-actin	g antiretroviral therapy?	
Stop date:									
			estion will show:						
Has the patie	nt restarted	ong-acting antire	troviral therapy?		YE	ES		NO	
	YES		NO						
Which long-ad		ive been given?	Reasons for	Which long-acti				Reasons for discontinuation	
long acting	2) long	3) long	discontinuation	long acting	2) long	•	3) long acting		
cabotegravir	acting	acting	(drop down	cabotegravir+	cabote	-	rilpivirine	*If death – please complete	
+ long	cabotegrav		menu with all	long acting	without		without	CoDe form	
acting	without	without	reasons in table	rilpivirine	rilpivirir	ne	cabotegravir	*If liver, other or unknown	
rilpivirine	rilpivirine	cabotegravir	3 in the					causes – please complete	
	• •	/ 600/900 mg	protocol)	Dosage: 400/60		B)/600/	900 mg (RPV)	hepatotoxicity form	
(RPV) (drop de	•			(drop down menu)			1		
Date of injecti			*If death —	Date of injection:			_		
	tended sche		please		ntended			1	
Monthly	Eve	y 2 Month	complete CoDe	Monthly		Every 2	Month		
			form						
			*If liver, other						
			or unknown						
			causes – please complete						
			hepatotoxicity						
			form						

(All those reported CAB + RPV discontinuations due to virological failure (reason 1, 1.1, 1.2) will prompt collection of resistance test results. A reminder will be sent after 1 and 2 years of follow up after failure. In addition to these specific reasons prompting collection of HIV resistance testing data, we will also perform checks for viral load>limit of detection to identify people with viral failure)

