6. RATIONALE AND BACKGROUND

6.1. Background

Cabotegravir (CAB), a human immunodeficiency virus type-1 (HIV-1) integrase strand transfer inhibitor (INSTI), in combination with Rilpivirine (RPV), an HIV-1 non-nucleoside reverse transcriptase inhibitor (NNRTI), is indicated as a complete regimen for the treatment of Human Immunodeficiency Virus type 1 (HIV-1) infection in adults who are virologically suppressed (HIV-1 RNA <50 copies/mL) on a stable antiretroviral (ART) regimen without present or past evidence of viral resistance to, and no prior virological failure with agents of the NNRTI and INSTI class. Prior to the initiation of CAB long acting (LA) injection, CAB tablets together with RPV tablets should be taken for approximately one month (at least 28 days) to assess tolerability to CAB and RPV.

Treatment with CAB+RPV LA should be prescribed by a physician experienced in the management of HIV infection. Each injection should be administered by a healthcare provider (HCP). Prior to starting the regimen, the HCP should carefully select individuals who agree to the required injection schedule and counsel individuals about the importance of adherence to scheduled dosing visits to help maintain virologic suppression and reduce the risk of viral rebound and potential development of resistance associated with missed doses. Following discontinuation of CAB+RPV LA injection, it is essential to adopt an alternative, fully suppressive ARV regimen per the summary of product characterization (SmPC).

The Marketing Authorization Holders (MAH) propose a five-year Drug Utilization Study (DUS) to be conducted in a real-world clinical setting. This prospective observational cohort study will aim to better understand the individual population receiving CAB and/or RPV LA containing regimens in routine clinical practice, usage patterns, adherence, post marketing clinical effectiveness of these regimens and monitor for resistance among virologic failures for whom data on resistance testing are available.

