7. RESEARCH QUESTIONS AND OBJECTIVE(S)

Following the initiation of any ARV regimen containing CAB and/or RPV LA among PLWH, the study will aim to assess usage patterns, durability, discontinuation, and virologic outcomes.

The specific objectives are to:

- 1. Describe CAB and/or RPV LA containing regimens usage patterns
 - Descriptive analysis of study population by baseline demographic and clinical characteristics
 - Monitor for use of oral lead-in
 - The potential regimen combinations are listed below (Note that CAB+RPV LA is the only approved regimen)
 - a. CAB+RPV LA regimen only
 - b. CAB LA monotherapy
 - c. CAB LA use in combination with ARVs other than RPV LA
 - d. RPV LA monotherapy
 - e. RPV LA use in combination with ARVs other than CAB LA
 - f. CAB LA+RPV LA+other ARVs
 - g. Combined group b-f
- 2. Assess adherence, durability and discontinuation for persons starting CAB+RPV LA regimen;
 - Proportion of individuals discontinuing the regimens of interest will be assessed.
 - Reasons for discontinuation will be assessed.
 - Non-adherence to the dosing schedule will be assessed by:
 - a. Estimating the number of individuals that missed one or more consecutive injections without taking daily oral bridging therapy or any other oral ARV regimen while not on CAB+RPV LA containing regimens and mean and median number of injections missed during a 12-month period
 - b. Estimating the number of individuals who received the injections seven or more days later than their scheduled injection visit and median duration of delayed injections
 - c. Estimating the number of individuals who missed one or more consecutive injections without taking daily oral bridging therapy or those who received the injections seven or more days later than their scheduled injection visit (Combined group a OR b) and describe patient characteristics for the individuals that are nonadherent.
 - Number of individuals with incorrect route of administration will be described.

- 3. Assess the clinical effectiveness (i.e. proportion of individuals experiencing virologic failure) among PLWH who initiate CAB+RPV LA regimen
 - a. Estimate the proportion of individuals with virologic failure, during the first 6 months after initiation of CAB+RPV LA
 - b. Estimate the proportion of individuals with virologic failure, at 6, 12 and 24 months after initiation of CAB+RPV LA
 - c. Stratified analyses for 3a and 3b will be conducted for VL at regimen initiation (<50 copies/mL and ≥50 copies/mL).

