8.3.1. Exposure definitions

The study period for data collection will start at the date of initiation of oral lead-in with CAB and/or RPV. The follow-up period for data analyses will start with first injection of CAB and/or RPV LA containing regimens and end at up to 48 months after discontinuation of the last injection.

Details about use of CAB and/or RPV LA containing regimens will be collected on a separate CRF. The data collected include dates of all planned and actual injections, use of oral bridging therapy for CAB+RPV LA, HIV subtype and resistance testing prior to initiation or at time of discontinuation of LA.

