Descriptive analyses will compare those with and without virologic success at 12, 24, 36 and 48 months after stopping the CAB+RPV LA regimen, as well as the next regimen started and time to start the next regimen following discontinuation of the regimen. If numbers allow for further analyses, multivariable logistic regression models will investigate the factors associated with virologic success at 12, 24, 36 and 48 months after switching off CAB+RPV LA regimen. Potential explanatory variables are listed above. Multivariate analyses will be performed when > 30 persons in the relevant treatment group have virologic success and analyses will be limited to persons with > 12 months follow-up. The model building strategy will follow EuroSIDA protocol and include variables significant in univariate analyses as well as *a priori* pre-specified variables of interest.

AIM 5. Evaluate the effectiveness of routine risk minimisation measures for regimen adherence, discontinuation due to incorrect route of administration and off-label use of CAB+RPV LA regimen

The purpose of this aim is to monitor to see if label guidance is adhered to, off label usage, adherence and discontinuation due to incorrect route of administration. This analysis on effectiveness of routine risk minimisation measures will be stratified for each region in the Eurosida cohort.

Analysis of off-label users – regimen combinations other than CAB+RPV LA (b -g in objective 1)

Descriptive Analysis:

As noted in Aim 1 above, analysis will be performed on the off-label users of CAB and/or RPV LA containing regimens. They will be characterized using demographics, clinical, immunologic and virologic characteristics at baseline (i.e. at initiation of regimen) stratified by different regimens noted in groups b-g above.

Adherence and Discontinuation:

Non-adherence to the dosing schedule and discontinuation due to incorrect route of administration will be assessed as described under Aim 2.

Clinical Outcomes:

Analysis will be conducted for the off-label users of CAB and/or RPV LA containing regimens separately to assess clinical outcome similar to description under Aim 3 above.

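### As written, Annex 1 gives people injected without an oral lead-in, or injected later after stopping one for another reason, no valid path to the injection fields, and cannot by itself show that a lead-in was omitted

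*Protocol*

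**What the plan says.** Section 7 lists, under Objective 1, "Monitor for use of oral lead-in". The label summary in Section 6.1 says that "CAB tablets together with RPV tablets should be taken for approximately one month (at least 28 days) to assess tolerability to CAB and RPV". Section 8.3.1 fixes the start of data collection: "The study period for data collection will start at the date of initiation of oral lead-in with CAB and/or RPV". It starts follow-up for analysis at the first injection. It also assigns planned and actual injection dates and oral bridging to a separate case report form.

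That form is in Annex 1. After HIV subtype it goes directly to the lead-in drug (cabotegravir or rilpivirine), its start date and its stop date. It then asks: "Was oral lead-in antiretroviral therapy stopped because the patient has initiated long-acting antiretroviral therapy". The two branches are "If yes, Treatment section below will open" and "If no, following will open"; what follows the second is a reason for discontinuation. Later injections depend on the first: "After completion of date of first injection, a new section will open for second injection".

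**The concern.** The question that leads to the injection record makes sense only for someone who took a lead-in. If the form is completed as written, a person who goes straight to injection has no true answer to give. A person who stopped the lead-in for, say, a supply reason and was injected later must answer *no*, and the injection section then does not open.

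Two things are at stake. One is the description of lead-in use under Objective 1, since the form has no way to record its absence. The other is the set of fields behind Aim 2: injection schedule, planned and actual dates, and bridging. Missed injections, delays of seven days or more, and the discontinuation date in Section 8.3.2 are all built from these. Any loss would fall on people selected by how their clinic starts the regimen, not at random.

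**Working it through.** The Protocol states no figure on this point, so the check traces the written branches and sets them beside the sections that use the data.

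**1. Branch trace in Annex 1**

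| Patient course | True answer to the lead-in question | What opens | Result on the form |
|---|---|---|---|
| Lead-in, then injection | yes | Treatment section | Captured |
| Lead-in, never injected | no | Reason for discontinuation | Captured |
| Lead-in stopped for another reason, injected later | no | Reason for discontinuation | Injections not captured; looks like a never-starter |
| Injected without lead-in | neither | Nothing, unless an untrue answer is given | Injections not captured, or a lead-in implied |

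**2. Are rows three and four in the study?** Yes. Section 8.2 takes new users from the date of starting the regimen and does not require a lead-in. Section 8.3.1 starts analysis follow-up at the first injection. However, it starts data collection at the lead-in, a date that people in row four do not have.

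**3. Is the missing item a pattern of the form?** No. The subtype, resistance-test, next-injection and bridging parts each ask a yes/no question first. The bridging part also asks whether long-acting therapy was later restarted. The lead-in part has neither an opening yes/no item nor a question about a later start.

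**4. Where row three would enter the analysis.** Sections 8.3.2 and 8.6 tabulate people who take the lead-in but never start the injections separately and leave them out of the primary analysis. Aim 2 also models not starting after a lead-in. On the form's data alone, a row-three person would be missing from the first analysis and counted as an event in the second.

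**5. What the form can show about lead-in.** It holds start and stop dates, so a lead-in shorter than the 28 days in Section 6.1 can be calculated. It has no value that means no lead-in was given.

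**6. Size.** The number affected is N × p, where p is the share of injected people in rows three and four. The Protocol gives no p. For illustration only, assume p from 5% to 20% and take the smallest and largest N in Table 4:

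- N = 100: 100 × 0.05 = 5, up to 100 × 0.20 = 20 people.
- N = 1000: 1000 × 0.05 = 50, up to 1000 × 0.20 = 200 people.

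These figures only show scale and are not estimates.

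**The case against.** The strongest reply is that this form is not the only data source. Section 8.2 says that it supplements routine collection and that the start and stop date of each antiretroviral is recorded. Table 2 lists the same dates with reasons for stopping, and Section 8.5.2 says that everything since the last data capture is supplied. A person with injections and no earlier oral cabotegravir or rilpivirine could be recognised there. This stands in part, with three limits:

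- The Protocol does not say that oral and long-acting forms are coded separately.
- An absent oral record does not distinguish none given from not recorded.
- Routine dates do not supply planned injection dates or bridging, which Section 8.3.1 assigns to this form.

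A second reply is that Annex 1 is an outline. It does not say that *yes* is the only route, and the built form may branch differently. That is fair: exclusivity is inferred from the absence of any other trigger.

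A reader might also infer more than the documents support:

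- *Lead-in use cannot be measured at all, and will always read 100%.* This could hold only for this form taken alone. Even there, a site could answer *yes* and leave the drug and dates blank, because nothing says that those fields are mandatory.
- *Direct starters drop out of the study.* They remain eligible and have routine data; what is at risk is their injection-level record.
- *Sites will invent lead-in dates.* This is conjecture about how sites would behave.
- *Aim 5 fails by its own benchmark.* Its opening words, "The purpose of this aim is to monitor to see if label guidance is adhered to", are broad, but the measures listed under Objective 5 in Section 7 do not include lead-in omission. A short lead-in is in any case detectable from the dates. The firm conflict is with Objective 1.

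**Conclusion.** The point holds as a fault in data capture. Followed as written, Annex 1 has no valid path to the injection fields for people injected without a lead-in, or for people injected later after stopping one for another reason. Both groups belong to the study population. The form alone cannot show that a lead-in was omitted, which conflicts with Objective 1, and it can make a late starter look like a never-starter.

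The size is unknown, since the Protocol gives no rate for either group. The conclusion assumes that the built form follows the branches in Annex 1. Routine drug dates may soften the loss on lead-in use, but not the loss of planned dates and bridging. An analysis plan cannot recover fields that were never opened, and Section 8.8 already warns that retrospective collection through additional forms may lower data quality. This makes it worth correcting before data entry.

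**What to change.** 1. At the top of the lead-in part of Annex 1, add *Was oral lead-in given? yes/no*. Let *no* open the Treatment section when an injection was given.
2. After a lead-in stopped for another reason, add *Was long-acting therapy started later? yes/no*. Let *yes* open the Treatment section.
3. In Section 8.3.1, start data collection at the lead-in or the first injection, whichever comes first.
4. Under Objective 1, report the proportion of injected people without a lead-in.

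The cost is two branching items, one amended sentence in Section 8.3.1 and one reporting line, with no extra visits or procedures. The change concerns recording only and takes no view on whether a lead-in should be used.

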8.2. Study Population and Setting

Study Population:

The study population will include PLWH over the age of 18 years, from EuroSIDA clinical sites who are new users of CAB and/or RPV LA containing regimens over a period of 5 years. Persons will be eligible for inclusion from the date of starting the treatment regimens after approval and commercial availability of the regimens. Only the first exposure to CAB and/or RPV LA containing regimens will be included in the primary analyses.

The potential regimen combinations are listed below (Note that CAB+RPV LA is the only approved regimen):

- a. CAB+RPV LA regimen only
- b. CAB LA monotherapy
- c. CAB LA use in combination with ARVs other than RPV LA
- d. RPV LA monotherapy
- e. RPV LA use in combination with ARVs other than CAB LA
- f. CAB LA+RPV LA+other ARVs
- g. Combined group b-f

EuroSIDA Cohort description:

The EuroSIDA study was initiated in 1994 and is a prospective observational cohort study of more than 22,000 individuals followed in over 100 hospitals in 34 European countries, and Israel and Argentina. The main objective of the study is to assess the impact of ARV drugs on the outcome of the general population of PLWH living in Europe.

In EuroSIDA, annual data collection is performed directly from clinics on individuals using comprehensive standardized clinical record forms via REDCap or electronic data transfer using the HICDEP format that includes information on outcomes and covariates [2]; further information is available at https://www.hicdep.org/. For each person, the date of starting and stopping each ARV drug is recorded. ATC codes for all ARVs and most non ARVs are collected. Dates of diagnosis of all AIDS defining diseases are recorded, using the 1993 clinical definition of AIDS from the Centers for Disease Control and Prevention. All EuroSIDA data undergo extensive data checks, queries and central clinical event validation to ensure a high quality and completeness of data.

Table 1. EuroSIDA currently contributing countries and geographical regions

Southern	Central Western	Northern Europe	Central Eastern	Eastern
Europe	Europe		Europe	Europe
Spain	France	United Kingdom	Poland	Estonia
Portugal	Belgium	Ireland	Czech Republic	Lithuania
Italy	Luxembourg	Netherlands	Bosnia-Herzegovina	Belarus
Greece	Switzerland	Denmark	Hungary	Ukraine
	Austria	Sweden	Romania	Russia
	Germany	Norway	Serbia	Georgia
		Finland	Slovenia	
		Iceland	Croatia	
*Israel			Albania	
*Argentina			North Macedonia	

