8.3.2. Outcome definitions

1.Regimen discontinuations: Discontinuation of CAB+RPV LA regimen for any reason during the study period will be captured, tabulated and reported.

Individuals who receive the oral lead-in but never initiate the CAB+RPV LA regimen will be tabulated separately but not included in the primary analysis.

Discontinuation of CAB +RPV LA will be defined as the latest date of the next scheduled injection which is missed and where bridging therapy has not been started. For example, for monthly dosing, if the first injection of CAB+RPV LA was received on June 1st, the second injection should be received on July 1st (allowed time window for second injection is June 24th to July 8th). The third injection should follow the timing of the first injection and should be received on August 1st (allowed time window for third injection is July 25th to August 8th). If not, date of discontinuation will be defined as August 8th (Monthly dosing).

For every 2 month dosing, if the first injection of CAB+RPV LA was received on June 1st, the second injection should be received on July 1st (allowed time window for second injection is June 24th to July 8th). The third injection should follow the timing of the first injection and should be received on September 1st (allowed time window for third injection is August 25th to September 8th). If not, date of discontinuation will be defined as September 8th (Every 2 month dosing).

Discontinuation will also be captured, tabulated and reported for any other CAB and/or RPV containing regimen.

Durability will be measured as proportion of individuals continuing on the regimen at the end of 6, 12 and 24 months.

Adherence will be assessed by estimating the number of individuals that missed one or more consecutive injections without taking daily oral bridging therapy or any other oral ARV regimen while not on CAB+RPV LA regimen and mean and median number of injections missed during a 12-month period. We will also estimate the number who received the injections seven or more days later than their scheduled injection visit and median duration of delayed injections in persons using bridging therapy.

In the standard follow-up data collection in EuroSIDA reasons for discontinuation are recorded as below.

Table 3. EuroSIDA – Reasons for Treatment Discontinuation

Code	Reason for Stopping Treatment
1	Treatment failure (i.e. virological, immunological, and/or clinical failure
1.1	Virological failure

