Descriptive analyses will compare those with and without virologic failure to assess any differences in baseline characteristics of the two groups. Detailed analysis of additional risk factors will be limited to persons with 6, 12 or 24 months of follow-up. Multivariable logistic regression models will investigate the factors associated with virologic failure at 6 months, 12 months and 24 months after CAB+RPV LA initiation. Potential explanatory variables are listed above. We will also investigate the impact of missed doses and use of oral bridging therapy by using the data collected via the CRF. Multivariate analyses will be performed when > 30 persons on CAB+RPV LA have virologic failure and analyses will be limited to persons with > 6-, 12- or 24-months follow-up. The model building strategy will follow EuroSIDA protocol and include variables significant in univariate analyses as well as *a priori* pre-specified variables of interest. Primary analysis for clinical effectiveness will include individuals on CAB+RPV LA, with VL of <50/copies/mL at regimen initiation. In addition, all the analyses will be conducted separately for individuals on CAB+RPV LA with VL of ≥50 copies/mL at regimen initiation.

Our primary analyses of virologic outcomes will censor follow-up at discontinuation of CAB+RPV LA, last visit or death, whichever occurs first, an on-treatment approach to analysis. Sensitivity analyses will use an intent to treat approach and virologic outcomes will be assessed regardless of regimen discontinuation.

We will perform additional sensitivity analysis limited to those who start CAB+RPV LA with resistance data available, to confirm no present or past evidence of viral resistance to, and no prior virological failure with agents of the NNRTI and INSTI class.

AIM 4. Monitor for resistance and next treatment response among individuals who switched off CAB+RPV LA regimen

Monitoring for resistance

Since this is a non-interventional study aiming to capture individual care in real world setting, the study will not mandate resistance testing following discontinuation of the regimen of interest. Health care providers following the local treatment guidelines decide

what laboratory and resistance tests are to be conducted. Data thus generated will be captured and analyzed by the study team.

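### On the two-month schedule, Annex 1 ends the first exposure when a late return exceeds its limit and makes no exception for oral bridging, while Section 8.3.2 counts the same bridged person as not discontinued.

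*Protocol*

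**What the plan says.** Section 8.3.2 of the protocol dates a discontinuation at the "latest date of the next scheduled injection which is missed and where bridging therapy has not been started". Bridging therefore prevents a discontinuation, and no maximum bridged gap is given.

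Annex 1 sets out what may follow a planned injection that is not given. In scenario 2 the person starts bridging, and "After end of bridging therapy there are three possibilities", the first being that injections resume. In scenario 3 there is no bridging, and the first outcome is again that injections resume. The text then states "The CRF will only capture the first exposure to LAI" and gives a time rule for the two-month schedule:

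- Second injection: "we will allow three months after the first injection to see if the regimen was resumed (≤2 months) or re-initiated (>2 months".
- Third and later injections: "we will allow four months after the second injection to see if the regimen was resumed (≤3 months) or re-initiated (>3 months". It adds: "In case of resumption of LAI after missed third injection in three months or less, we still consider it first exposure".

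The rule does not mention bridging, and no such limit is given for the monthly schedule.

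Section 8.2 states: "Only the first exposure to CAB and/or RPV LA containing regimens will be included in the primary analyses". Section 8.6, Aim 3, adds: "We will also investigate the impact of missed doses and use of oral bridging therapy by using the data collected via the CRF".

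**The concern.** Two rules decide whether a person is still in their first course of CAB+RPV LA, and they use different criteria. Section 8.3.2 asks whether a missed injection was bridged. Annex 1 asks only how long the return took. For a bridged person who returns after the Annex 1 limit, the answers differ.

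That status feeds several results. Durability is the proportion continuing at 6, 12 and 24 months. The primary virologic analysis in Section 8.6 censors at discontinuation, last visit or death. The primary analyses as a whole are limited to the first exposure. With two answers in the protocol, a virologic failure after a bridged return could be counted by one analyst and left out by another. The effect of bridging is itself studied under Aims 2, 3 and 4, so the people whose status is unclear are among those whose outcomes these aims need. The conflict also touches data collection: an injection date that is never collected cannot be restored by a later analysis plan.

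**Working it through.** **Does the Annex 1 rule reach bridged gaps?** It follows directly after scenarios 2 and 3, both of which contain a resumption outcome, and it carries no exception. It is triggered by a missed injection. In this protocol an injection can be missed while bridged: Aim 2 in Section 8.6 plans a comparison among people who miss injections with bridging in use. As written, the rule covers both scenarios.

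**Reproducing the protocol's own date.** In the 8.3.2 example for two-monthly dosing, injections are given on 1 June and 1 July and the third is due on 1 September. Window end = due date + 7 days = 8 September, which matches the stated discontinuation date for a missed, unbridged injection.

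**Third and later injections.** Take the same dates.

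- Last injection 1 July; due date = last + 2 months = 1 September.
- Limit counted from the last injection = 1 July + 3 months = 1 October, which is 30 days past due.
- Annex 1 look-ahead = 1 July + 4 months = 1 November.
- Next scheduled date if the third injection is skipped = 1 September + 2 months = 1 November, so 4 months from the last injection.
- 4 > 3, so a return on the next scheduled date is a re-initiation under Annex 1. Under 8.3.2, with bridging started, there is no discontinuation.

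An earlier return gives the same conflict. A person bridged from 1 September and injected on 15 October is 106 days from the last injection and 44 days past due: not discontinued under 8.3.2, re-initiated under Annex 1.

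**Could the 3 months run from the missed due date?** The limit would then be 1 September + 3 months = 1 December. That is later than the look-ahead end of 1 November, so the rule could never be applied within its own observation period. For third and later injections, only the count from the last injection is coherent.

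**Second injection.** First injection 1 June, second due 1 July, look-ahead end 1 June + 3 months = 1 September, which is also the target date for the third injection.

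| Origin of the 2 months | Limit | Return on 1 September |
|---|---|---|
| Last injection (1 June) | 1 August, 31 days past due | 3 > 2: re-initiated |
| Missed due date (1 July) | 1 September | 2 ≤ 2: resumed |

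Both readings fit the look-ahead, so the wording does not settle the matter.

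**What is recorded after return?** Annex 1 confines the form to the first exposure. Further on, it says that every injection up to 24 months plus six weeks after initiation is collected, and its bridging branch has restart fields (drugs, dosage, date, schedule) with no time limit. These statements agree only if a bridged return stays within the first exposure.

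**The case against.** The strongest reply is that Annex 1 never says the limit applies to bridged gaps. The rule stands straight after scenario 3, which asks about later restarts, and can be read as fixing how long to wait for one. Re-initiation may be taken to presuppose a discontinuation, which 8.3.2 rules out under bridging. Section 8.3.2 dates discontinuations and does not define exposure episodes. This is a possible reading, and probably a sensible intention. But the text does not state it, and the shared resumption outcome and the protocol's own use of missed injections point the other way.

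A reader might infer more than the documents support:

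- *That such people drop out, or lose all their later injection records.* Their data before the return remain in any case. Section 8.3.1 lists all planned and actual injection dates, and Annex 1 elsewhere promises collection to 24 months plus six weeks. Loss of injection records after return is a risk arising from conflicting statements, not a certainty.
- *That Aims 2 to 4 would see only bridges ending within a month of the due date.* The form records bridging start and stop dates whatever follows.
- *That virologic failures after return are lost.* Viral loads are routine EuroSIDA data (Section 8.3, Table 2), and Section 8.5.2 has all results since the last capture supplied. Aim 3 does not censor at re-initiation, and its sensitivity analysis ignores discontinuation.
- *That bridging is judged on its safest uses.* Nothing in the protocol ranks bridges by risk.

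**Conclusion.** The point stands as a contradiction in classification, limited to the two-month schedule. For third and later injections, skipping one under bridging and returning on the next scheduled date makes a person continuing under 8.3.2 and re-initiated under Annex 1. The longest bridged gap that Annex 1 keeps within the first exposure is 3 − 2 = 1 month past due, half of one dosing interval. For the second injection the same conflict arises only if the count runs from the last injection.

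What is in doubt is the status of time after return, and possibly its injection records. The protocol gives no frequency of bridging, so the number affected is unknown. Purely as an illustration, take 500 starters, one of the sample sizes in Table 4 of Section 8.4, and assume that all are on the two-month schedule. If 5% bridge one full interval at a third or later injection, 0.05 × 500 = 25 people would have conflicting status; 2% to 10% gives 10 to 50. The conclusion rests on reading the Annex rule as covering scenario 2, which its placement and silence support but which it does not say outright. The text should be corrected before it governs form logic.

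**What to change.** Reconcile Sections 8.2 and 8.3.2 with Annex 1, for data capture and analysis only:

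1. State that the resumed/re-initiated limit does not end the first exposure of a person whom 8.3.2 counts as not discontinued because of documented bridging. One simple way is to apply the limit to scenario 3 only.
2. State whether the 2 and 3 months run from the last injection or from the missed due date.
3. Confirm that collection of injections to 24 months plus six weeks continues after a bridged return, and word the first-exposure restriction on the form to match.

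The cost is about a sentence for each item, one change to the form's skip logic, and additional injection records for bridged people who return. This classifies records. It sets no clinical limit on bridging and changes no care.
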